7.0 TRIAL PROCEDURES

7.1 Trial Procedures

The Trial Flow Chart - Section 6.0 summarizes the trial procedures to be performed at each visit. Individual trial procedures are described in detail below. It may be necessary to perform these procedures at unscheduled time points if deemed clinically necessary by the investigator.

Furthermore, additional evaluations/testing may be deemed necessary by the Sponsor and/or Merck for reasons related to subject safety. In some cases, such evaluation/testing may be potentially sensitive in nature (e.g., HIV, Hepatitis C, etc.), and thus local regulations may require that additional informed consent be obtained from the subject. In these cases, such evaluations/testing will be performed in accordance with those regulations.

7.1.1 Administrative Procedures

7.1.1.1 Informed Consent

The Investigator must obtain documented consent from each potential subject prior to participating in a clinical trial.

7.1.1.1.1 General Informed Consent

Consent must be documented by the subject's dated signature or by the subject's legally acceptable representative's dated signature on a consent form along with the dated signature of the person conducting the consent discussion.

A copy of the signed and dated consent form should be given to the subject before participation in the trial.

The initial informed consent form, any subsequent revised written informed consent form and any written information provided to the subject must receive the IRB/ERC's approval/favorable opinion in advance of use. The subject or his/her legally acceptable representative should be informed in a timely manner if new information becomes available that may be relevant to the subject's willingness to continue participation in the trial. The communication of this information will be provided and documented via a revised consent form or addendum to the original consent form that captures the subject's dated signature or by the subject's legally acceptable representative's dated signature.

Specifics about a trial and the trial population will be added to the consent form template at the protocol level.

The informed consent will adhere to IRB/ERC requirements, applicable laws and regulations and Sponsor requirements.

7.1.1.2 Inclusion/Exclusion Criteria

All inclusion and exclusion criteria will be reviewed by the investigator or qualified designee to ensure that the subject qualifies for the trial.

7.1.1.3 Medical History

A medical history will be obtained by the investigator or qualified designee. Medical history will include all active conditions, and any condition diagnosed within the prior 10 years that are considered to be clinically significant by the Investigator. Details regarding the disease for which the subject has enrolled in this study will be recorded separately and not listed as medical history.

7.1.1.4 Prior and Concomitant Medications Review

7.1.1.4.1 Prior Medications

The investigator or qualified designee will review prior medication use, including any protocol-specified washout requirement, and record prior medication taken by the subject within 28 days before starting the trial. Treatment for the disease for which the subject has enrolled in this study will be recorded separately and not listed as a prior medication.

7.1.1.4.2 Concomitant Medications

The investigator or qualified designee will record medication, if any, taken by the subject during the trial. All medications related to reportable SAEs and ECIs should be recorded as defined in Section 7.2.

7.1.1.5 Disease Details and Treatments

7.1.1.5.1 Disease Details

The investigator or qualified designee will obtain prior and current details regarding disease status.

7.1.1.5.2 Prior Treatment Details

The investigator or qualified designee will review all prior cancer treatments including systemic treatments, radiation and surgeries.

7.1.1.5.3 Subsequent Anti-Cancer Therapy Status

Not applicable.

7.1.1.6 Assignment of Screening Number

Not applicable.

7.1.1.7 Assignment of Randomization Number

Not applicable.

7.1.1.8 Trial Compliance (Medication/Diet/Activity/Other)

Patients will be instructed to comply to study visits and concomitant medications by the research staff and compliance.

7.1.2 Clinical Procedures/Assessments

Response assessment will formally be conducted after 6 cycles of pembrolizumab therapy, This will include assessment of symptoms, hematologic profile, bone marrow histomorphologic abnormalities, spleen length by manual palpation on physical exam, cytogenetics, and changes in mutational burden from baseline measurement. These established consensus criteria (ELN-IWG) shown in TABLE 5 will allow for uniformity in response assessment and are standardized.

7.1.2.1 Adverse Event (AE) Monitoring

The investigator or qualified designee will assess each subject to evaluate for potential new or worsening AEs as specified in the Trial Flow Chart and more frequently if clinically indicated. Adverse experiences will be graded and recorded throughout the study and during the follow-up period according to NCI CTCAE Version 4.0 (see Section 11.2). Toxicities will be characterized in terms regarding seriousness, causality, toxicity grading, and action taken with regard to trial treatment.

For subjects receiving treatment with pembrolizumab all AEs of unknown etiology associated with pembrolizumab exposure should be evaluated to determine if it is possibly an event of clinical interest (ECI) of a potentially immunologic etiology (termed immune-related adverse events, or irAEs).

Please refer to section 7.2 for detailed information regarding the assessment and recording of AEs.

7.1.2.2 Full Physical Exam

The investigator or qualified designee will perform a complete physical exam during the screening period. Clinically significant abnormal findings should be recorded as medical history. A full physical exam should be performed during screening, and at each study visit as indicated in the trial flow chart.

7.1.2.2.1 MPN-SAF TSS

The investigator or qualified designee will use the MPN-SAF TSS measure at every study visit to assess constitutional symptoms as part of the interval history assessment.

7.1.2.3 Vital Signs

The investigator or qualified designee will take vital signs at screening, prior to the administration of each dose of trial treatment and at treatment discontinuation as specified in the Trial Flow Chart (Section 6.0). Vital signs should include temperature, pulse, respiratory rate, weight and blood pressure. Height will be measured at screening only.

7.1.2.4 Eastern Cooperative Oncology Group (ECOG) Performance Scale

The investigator or qualified designee will assess ECOG status (see Section 11.1) at screening, prior to the administration of each dose of trial treatment and discontinuation of trial treatment as specified in the Trial Flow Chart.

7.1.2.5 Assessment of Disease Response

Clinical response for patients with MF-CP in the primary cohort will be evaluated using the Revised IWG-MRT and ELN response criteria for Myelofibrosis¹² as follows (patients must achieve at least CI to continue in the extension phase):

TABLE 5. International Working Group for Myelofibrosis Research and Treatment and European leukemiaNet (IWG-ELN) response criteria for myelofibrosis

Response categories	Required criteria (for all response categories, benefit must last for ≥12 weeks in order to qualify as a response)
Complete Remission (CR)	Bone marrow: * Age-adjusted normocellularity; <5% blasts; ≤Grade 1 myelofibrosis**, AND Peripheral blood: Hemoglobin ≥100 g/L and <UNL; Neutrophil count ≥1 x 10 ⁹ /L and <UNL; Platelet count ≥100 x 10 ⁹ /L and <UNL; <2% immature myeloid cells***, AND Clinical: Resolution of disease symptoms; Spleen and liver not palpable; No evidence of EMH
Partial Remission (PR)	Peripheral blood: Hemoglobin ≥100 g/L and <UNL; Neutrophil count ≥1 x 10 ⁹ /L and <UNL; Platelet count ≥100 x 10 ⁹ /L and <UNL; <2% immature myeloid cells***, AND Clinical: Resolution of disease symptoms; Spleen and liver not palpable; No evidence of EMH OR Bone marrow: * Age-adjusted normocellularity; <5% blasts; ≤Grade 1 myelofibrosis**, AND Peripheral blood: Hemoglobin ≥85 but <100 g/L and <UNL; Neutrophil count ≥1 x 10 ⁹ /L and <UNL; Platelet count ≥50 but <100 x 10 ⁹ /L and <UNL; <2% immature myeloid cells***, AND Clinical: Resolution of disease symptoms; Spleen and liver not palpable; No evidence of EMH
Clinical improvement (CI)	The achievement of anemia, spleen or symptoms response without progressive disease or increase in severity of anemia, thrombocytopenia or neutropenia‡
Anemia response	Transfusion-independent patients: a ≥20 g/L increase in hemoglobin level† Transfusion-dependent patients: becoming transfusion-independent††
Spleen response§	A baseline splenomegaly that is palpable at 5-10 cm, below the LCM, becomes not palpable§§, OR A baseline splenomegaly that is palpable at >10 cm, below the LCM, decreases by ≥50%§§ A baseline splenomegaly that is palpable at <5 cm, below the LCM, is not eligible for spleen response

	A spleen response requires confirmation by MRI or CT showing $\geq 35\%$ spleen volume reduction
Symptoms response	A $\geq 50\%$ reduction in the Myeloproliferative Neoplasm Symptom Assessment Form total symptom score (MPN-SAF TSS) ^g
Progressive disease^h	Appearance of a new splenomegaly that is palpable at least 5 cm below the LCM, OR A $\geq 100\%$ increase in palpable distance, below LCM, for baseline splenomegaly of 5 to 10 cm, OR A 50% increase in palpable distance, below LCM, for baseline splenomegaly of >10 cm, OR Leukemic transformation confirmed by a bone marrow blast count of $\geq 20\%$, OR A peripheral blood blast content of $\geq 20\%$ associated with an absolute blast count of $\geq 1 \times 10^9/L$ that lasts for at least two weeks
Stable disease	Belonging to none of the above listed response categories
Relapse	No longer meeting criteria for at least CI after achieving CR, PR or CI, OR Loss of anemia response persisting for at least one month, OR Loss of spleen response persisting for at least one month

Response assessment for patients with MPN-BP disease will follow the standard response assessment for AML defined by Cheson et al¹³ as shown in Table 6A (patients must achieve at least a PR to continue to extension phase).

Table 6A. Acute Myeloid Leukemia Response Assessment Criteria

Complete Response (CR)
The subject must be free of all symptoms related to leukemia and have an absolute neutrophil count of greater than $1 \times 10^9/L$, no need for red blood cell transfusion, platelet count greater than $100 \times 10^9/L$, and normal marrow differential ($<5\%$ blasts) in a normo- or hypercellular marrow
Cri
As per CR but incomplete count recovery
Partial Response
CR with 6-25% abnormal cells in the marrow or 50% decrease in bone marrow blasts

Additionally, response assessment for patients with accelerated or blast phase disease will be measured by published consensus criteria by Mascarenhas et al. specifically designed for MPN-AP/BP as shown in Table 6B. These criteria will also be utilized as there are no current standardized response criteria for MPN-AP or BP. These criteria are based on hematological, pathological, clinical, cytogenetic and molecular responses. These criteria incorporate established response criteria for AML, MDS and MPN.

TABLE 6B. Formal response assessment categories for MPN-AP/BP

Complete molecular response (CMR)	
Description	Complete remission of both leukemia and MPN without detectable molecular markers associated with either leukemia or MPN
Hematologic profile	ANC > 1000 Hemoglobin > 10 g/dL Platelets > 100 × 10 ⁹ /L Absence of leukoerythroblastosis ^a
Spleen	Non-palpable
Bone marrow	Cellularity appropriate for age Resolution of abnormal morphology Blasts ≤ 5% ^b ≤Grade 1 marrow fibrosis
Cytogenetics	Normal karyotype ^c
Molecular markers	Loss of any previously documented markers associated with either the leukemic or MPN clone ^d
Complete cytogenetic response (CCR)	
Description	Complete remission of both leukemia and MPN with detectable molecular markers associated with either leukemia or MPN
Hematologic profile	ANC > 1000 Hemoglobin > 10 g/dL Platelets > 100 × 10 ⁹ /L Absence of leukoerythroblastosis ^a
Spleen	Non-palpable
Bone marrow	Cellularity appropriate for age Resolution of abnormal morphology Blasts ≤ 5% ^b ≤Grade 1 marrow fibrosis
Cytogenetics	Normal karyotype ^c
Molecular markers	Residual expression of MPN/leukemia associated gene mutations (e.g. JAK2V617F, MPL515L/K) ^d
Acute leukemia response-complete (ALR-C)	
Description	Complete remission of leukemia with residual MPN features
Hematologic profile	Absence of blasts ^a
Spleen	<25% increase in spleen size by palpation or imaging if baseline spleen <10 cm or <50% if baseline spleen ≥10 cm
Bone marrow	Blasts ≤ 5% ^b
Cytogenetics	Loss of cytogenetic abnormality associated with leukemic clone, may have persistent abnormality associated with MPN
Molecular markers	Loss of any previously identified markers in leukemic clone, may have persistent molecular markers associated with MPN ^d

Acute leukemia response-partial (ALR-P)	
Description	Decrease in leukemic burden but without resolution of peripheral blood or bone marrow blasts and residual MPN features
Hematologic profile	>50% reduction in blasts
Spleen	<25% increase in spleen size by palpation or imaging if baseline spleen <10 cm or <50% if baseline spleen ≥10 cm
Bone marrow	>50% reduction in blasts
Cytogenetics	No new abnormalities
Molecular markers	No new abnormalities
Stable disease (SD)	
Description	Failure to achieve at least LR-P, but no evidence of progression for at least 8 weeks
Progressive disease (PD)	
Description	Progression of leukemia and/or background MPN
Hematologic profile	For patients with 10-20% blasts: ≥50% increase to >20% blasts For patients with >20% blasts: ≥50% increase to >30% blasts
Spleen	>25% increase in spleen size by palpation or imaging if baseline spleen <10 cm and >50% if baseline spleen ≥10 cm
Bone marrow	For patients with 5–10% blasts: ≥50% increase to >10% blasts For patients with 10–20% blasts: ≥50% increase to >20% blasts For patients with >20% blasts: ≥50% increase to >30% blasts
Cytogenetics	Does not apply
Molecular markers	Does not apply

- a. Absence of peripheral blood blasts by morphologic review of the peripheral smear on two occasions separated by at least 2 weeks.
- b. Blast percentage can be assessed by morphologic review of aspirate and in cases of inaspirate marrows, immunohistochemical staining of the marrow for CD34+, CD117+ is acceptable.
- c. Normal karyotype by conventional cytogenetics in peripheral blood or bone marrow aspirate, if a cytogenetic abnormality is detected prior to treatment it must not be identified at time of assessment; if an abnormality is detected at baseline by FISH it must be absent by FISH at time of assessment.
- d. Absence or loss of evidence of mRNA transcript by quantitative PCR assay performed in a validated laboratory, this will also include any exploratory biomarkers determined to be positive prior to therapy

7.1.3 Laboratory Procedures/Assessments

Details regarding specific laboratory procedures/assessments to be performed in this trial are provided below. Laboratory Safety Evaluations (Hematology, Chemistry and Urinalysis)

Laboratory tests for hematology, chemistry, urinalysis, and others are specified in Table 9.

Table 9. Laboratory Tests

Hematology	Chemistry	Urinalysis	Other
Hematocrit	Albumin	Blood	Serum β -human chorionic gonadotropin [†]
Hemoglobin	Alkaline phosphatase	Glucose	(β -hCG) [†]
Platelet count	Alanine aminotransferase (ALT)	Protein	PT (INR)
WBC (total and differential)	Aspartate aminotransferase (AST)	Specific gravity	aPTT
Red Blood Cell Count	Lactate dehydrogenase (LDH)	Microscopic exam (If abnormal)	Total triiodothyronine (T3)
Absolute Neutrophil Count	Carbon Dioxide † (CO ₂ or bicarbonate)	results are noted	Free tyroxine (T4)
Absolute Lymphocyte Count [†]	Creatinine	Urine pregnancy test [†]	Thyroid stimulating hormone (TSH)
MCV	Uric Acid		Blood for correlative studies
NRBC	Calcium		
	Chloride		
	Glucose		
	Phosphorus		
	Potassium		
	Sodium		
	Magnesium		
	Total Bilirubin		
	Direct Bilirubin (If total bilirubin is elevated above the upper limit of normal)		
	Total protein		

Hematology	Chemistry	Urinalysis	Other
	Blood Urea Nitrogen		

† Perform on women of childbearing potential only. If urine pregnancy results cannot be confirmed as negative, a serum pregnancy test will be required.
 
‡ If considered standard of care in your region.
 
⌣ This value may be manually calculated.
			

Laboratory tests for screening or entry into the Core Treatment Phase should be performed within 28 days prior to the first dose of treatment. After Cycle 1, pre-dose laboratory procedures can be conducted up to 72 hours prior to dosing. Results must be reviewed by the investigator or qualified designee and found to be acceptable prior to each dose of trial treatment.

7.1.3.1 Pharmacodynamic Evaluations

The pharmacodynamic studies performed in this trial are incorporated in the exploratory objectives and listed in TABLE 8. These include assessing PD-1/L1 expression levels in different cellular compartments in the blood and bone marrow as discussed above as well as determining treatment effect on the malignant clone by assessment of changes in driver mutation levels and histomorphologic changes in the bone marrow of treated patients.

7.1.3.1.1 Blood Collection for Serum Pembrolizumab

Sample collection, storage and shipment instructions for serum samples will be provided in the Laboratory Manual.

This will not be assayed in this trial.

7.1.3.1.2 Blood Collection for Anti-Pembrolizumab Antibodies

This will not be assayed in this trial.

7.1.4 Other Procedures

No other intended procedures.

7.1.4.1 Withdrawal/Discontinuation

When a subject discontinues/withdraws prior to trial completion, all applicable activities scheduled for the final trial visit should be performed at the time of discontinuation. Any adverse events which are present at the time of discontinuation/withdrawal should be followed in accordance with the safety requirements outlined in Section 7.2 - Assessing and Recording Adverse Events. Subjects who do not attain at least CI (MF-CP) or PR (MPN AP/BP). Subjects who attain a CR by IWG-ELN criteria after 6 cycles of therapy with pembrolizumab may discontinue treatment. After discontinuing treatment following assessment of CR, these subjects should return to the site for a Safety Follow-up Visit 30 days post last dose. (described in Section 7.1.5.3.1).

7.1.4.2 Blinding/Unblinding

Not applicable.

7.1.5 Visit Requirements

Visit requirements are outlined in Section 6.0 - Trial Flow Chart. Specific procedure-related details are provided above in Section 7.1 - Trial Procedures.

7.1.5.1 Screening

Subjects who are candidates for enrollment into the study will be evaluated for eligibility by the Investigator to ensure that the inclusion and exclusion criteria have been satisfied and that the subject is eligible for participation in this clinical study. The Study Chairs will confirm eligibility for all subjects prior to receipt of the first dose of pembrolizumab.

7.1.5.1.1 Screening Period

The screening period will begin after signed consent is obtained and will last for 28 days (Day -28 to day -1). During this period Inclusion and exclusion criteria will be reviewed by the PI and this will include the following tests and procedures to be completed: demographics and medical history, prior con med review, physical exam with attention to spleen length in craniocaudal direction measured by a ruler at the mid clavicular line from the costal margin, vitals, ECOG, CBC and comprehensive serum chemistry, PT/PTT, serum or urine HCG, urinalysis, thyroid function tests, Chest X ray (PA and lateral), bone marrow biopsy and aspiration, flow cytometry and cytogenetics (if aspirate is not obtained then will be done from the peripheral blood). Biomarkers from the peripheral blood and aspirate will also be collected as outlined in the biomarker section of this protocol and delineated in the Biomarker table.

7.1.5.2 Treatment Period

The treatment period will consist of 3 week cycles in which the study drug will be given on day 1 of each cycle and the following tests and procedures will be obtained: prior con med review, adverse event review, physical exam with attention to spleen length in craniocaudal direction measured by a ruler at the mid clavicular line from the costal margin, vitals, ECOG, CBC and comprehensive serum chemistry, and thyroid function tests (on C3D1).

The core study period is a total of 6 cycles (study visits and drug administration will take place on day 1 of each cycle and the window is +/- days). Response assessment visit will take place on cycle 7 day 1 which will include the addition of a bone marrow biopsy and aspiration and biomarker evaluation from the aspirate and peripheral blood. The PI will decide if the subject will continue receiving therapy in the extension phase (Cycle 7+) of the trial as long the following is true: at least a clinical improvement by IWG-ELN criteria (Table 5) for chronic phase patients and at least a partial response by Table 6A and 6B (secondary objective) for accelerated and blast phase patients; the absence of unacceptable toxicity; both patient and treating physician are in favor of continued treatment on protocol. Patients can continue receiving study drug in the extension phase as long as they do not meet criteria for discontinuation of treatment defined in Section 5.8 and to a maximum duration of 2 years

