2.1 Trial Design

This is a multicenter, open-label, Phase 2 study to assess the efficacy, safety and tolerability of pembrolizumab in patients with chronic phase myelofibrosis (MF-CP) defined as either patients with primary myelofibrosis (PMF), post essential thrombocythemia (post-ET) or polycythemia vera (post-PV) myelofibrosis (primary cohort). We propose a Simon-two stage design for this study. We will test pembrolizumab at the FDA approved dose (in head and neck cancer) of 200mg dose administered via intravenous infusion over 30 minutes given every 3 weeks. Nine patients will be enrolled in the first stage of the Simon-two stage design, and 15 in the second stage. A treatment cycle is 3 weeks and the core study period is 6 cycles. Response assessment by established consensus criteria will be used to assess response after 6 cycles in order to determine if the trial will progress to the second stage and for the purpose of determining the primary endpoint. In addition, we will allow a maximum of ten patients with accelerated or blast phase disease (MPN-AP/BP) who are refractory or intolerant to conventional therapies such as decitabine, and in which hematopoietic stem cell transplant is not a therapeutic option (exploratory cohort), to enroll in the study as a separate exploratory cohort. These patients can be enrolled during stage 1 or 2 and they will be analyzed separately from the primary cohort population. The study will therefore enroll a maximum of 34 patients.

The study will enroll at 3 centers (Mount Sinai, NY; Montefiore, NY; Massachusetts General Hospital, MA).

Exploratory biomarkers will be obtained from enrolled patients at baseline, cycle 3 and cycle 7 and at 1 year of therapy. Patients that obtain at least a clinical improvement after 6 cycles of therapy can continue receiving pembrolizumab until evidence of disease progression, unacceptable toxicity, and patient or physician decision for a maximum of 2 years.

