5.8 Subject Withdrawal/Discontinuation Criteria

Subjects may withdraw consent at any time for any reason or be dropped from the trial at the discretion of the investigator should any untoward effect occur. In addition, a subject may be withdrawn by the investigator or the Sponsor if enrollment into the trial is inappropriate, the trial plan is violated, or for administrative and/or other safety reasons. Specific details regarding discontinuation or withdrawal are provided in Section 7.1.4 – Other Procedures.

A subject must be discontinued from the trial for any of the following reasons:

- The subject or legal representative (such as a parent or legal guardian) withdraws consent.
- Unacceptable adverse experiences as described in Section 5.2.1.2
- Subject did not achieve at least a CI response per Table 5 for the MF-CP cohort or at least PR for the MPN-AP/BP cohort per Table 6A at response assessment.

- Intercurrent illness that prevents further administration of treatment
- Investigator's decision to withdraw the subject
- The subject has a confirmed positive serum pregnancy test
- Noncompliance with trial treatment or procedure requirements
- The subject is lost to follow-up
- Administrative reasons

The End of Treatment and Follow-up visit procedures are listed in Section 6 (Protocol Flow Chart) and Section 7.1.5 (Visit Requirements). After the end of treatment, each subject will be followed for 30 days for adverse event monitoring (serious adverse events will be collected for 90 days after the end of treatment as described in Section 7.2.3.1).

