^f Comprehensive Serum Chemistry Panel should include the following: Albumin, Alkaline phosphatase, Glucose, Alanine aminotransferase (ALT), Aspartate aminotransferase (AST), Lactate dehydrogenase (LDH), (CO₂ or bicarbonate), Uric Acid, Calcium, Chloride, Glucose, Phosphorus, Potassium, Sodium, Magnesium, Total Bilirubin, Direct Bilirubin (If total bilirubin is elevated above the upper limit of normal), Total protein, Blood Urea Nitrogen

^g Flow cytometry for acute leukemia panel and cytogenetics will be sent from the bone marrow aspirate, if this is not obtainable then will be sent from the peripheral blood to be performed locally at study site

^h If it is known, prior to C7D1, that the patient will not achieve the required response, CI, for continuation, the C7D1 and End of Treatment visit will be combined. All study activities for C7D1 will be done except dosing of the study medication.

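### The response an accelerated- or blast-phase patient needs to continue after cycle 6 is stated inconsistently, and the marrow band of Table 6A PR can be met with unchanged blasts

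*Combined protocol and SAP*

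**What the plan says.** The decision is whether an MPN-AP/BP patient (the exploratory cohort, at most 10) goes on to cycle 7 and beyond, for up to 2 years. The document states the required response in several places:

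- **Section 5.8** lists, among the reasons for mandatory discontinuation, not achieving "at least PR for the MPN-AP/BP cohort per Table 6A at response assessment".
- **Section 7.1.5.2** lets accelerated and blast phase patients continue with "at least a partial response by Table 6A and 6B (secondary objective").
- **Section 7.1.2.5** introduces Table 6A with "Response assessment for patients with MPN-BP disease will follow the standard response assessment for AML" and attaches the gate there: "patients must achieve at least a PR to continue to extension phase". Table 6B follows as an additional measure for AP and BP, with no continuation rule.
- **Section 7.1.4.1** gives PR for AP/BP without a table, in a sentence that has no main clause.
- **Section 2.1** says "Patients that obtain at least a clinical improvement after 6 cycles of therapy can continue receiving pembrolizumab" and names no cohort. Footnote h of the flow chart (section 6.1), repeated in section 7.1.5.3.1, speaks of knowing before C7D1 "that the patient will not achieve the required response, CI, for continuation".

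Table 6A defines partial response as "CR with 6-25% abnormal cells in the marrow or 50% decrease in bone marrow blasts". The lowest response in Table 6B is ALR-P, which needs more than a 50% blast reduction in the hematologic profile and in the marrow. Section 5.1.2 admits AP/BP patients at 10% or more blasts in peripheral blood or bone marrow.

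**The concern.** There are two separate problems.

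First, the gate differs by section in the table used and in the patients it covers. Section 7.1.5.2 cannot be applied as written, because one of its two tables lacks the category it names. Accelerated-phase patients are under the Table 6A gate in section 5.8 and outside it in section 7.1.2.5. No section is said to prevail.

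Second, one limb of Table 6A PR is an absolute marrow range with no reference to baseline, and much of the range in which this cohort may enter lies inside it. A patient may therefore meet the blast part of the continuation criterion without any fall in marrow blasts.

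At stake is which patients receive pembrolizumab in the extension. That decides extension exposure and which patients contribute later marrow samples. Sites could apply the gate differently in a very small cohort.

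**Working it through.** The plan gives no figure to reproduce here. The check sets the rules side by side and then enumerates marrow-blast values.

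**1. The gate by section**

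| Section | Category | Table | Patients named |
|---|---|---|---|
| 5.8 | PR | 6A | AP and BP |
| 7.1.5.2 | partial response | 6A and 6B | AP and BP |
| 7.1.2.5 | PR | 6A | BP only |
| 7.1.4.1 | PR | none named | AP and BP |
| 2.1, 7.1.5.3.1, footnote h | CI | none named (CI exists only in Table 5) | no cohort named |

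**2. Inputs for the marrow-blast component**

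Let b be baseline and f the post-cycle-6 marrow blast percentage, in whole percents.

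- Table 6A PR (section 7.1.2.5): 6 ≤ f ≤ 25, or f ≤ 0.5b.
- Table 6B ALR-P (same section): f < 0.5b.
- Table 6B marrow progression for baseline 10-20%: f ≥ 1.5b and f > 20.
- Entry (section 5.1.2): 10% or more in blood or marrow. The eligibility criteria give no boundary between AP and BP, so I ran AP as 10-19% and as 10-20%. The second is the band Table 6B uses.

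**3. Unchanged marrow blasts (f = b)**

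| Baseline | Meets 6A PR marrow part | Meets ALR-P marrow part |
|---|---|---|
| 10-19% | 10 of 10 | 0 of 10 |
| 10-20% | 11 of 11 | 0 of 11 |
| 20-25% | 6 of 6 | 0 of 6 |
| 26-90% | 0 of 65 | 0 of 65 |

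Over 10-25% this is 10 + 6 = 16 of 16 for Table 6A and 0 of 16 for ALR-P. For example, 12% before and 12% after is inside 6-25% with a reduction of 0%.

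**4. Other discordant values**

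- Rising blasts: with baseline 10-19%, 30 baseline/follow-up pairs (baselines 10-16%) lie in the 6A band while meeting Table 6B marrow progression. One is 11% to 22%: 22/11 = 2.0, at least 1.5, and 22 > 20.
- Exactly 50%: 40% to 20% meets 6A, but not the more-than-50% rule of ALR-P.
- Smaller fall: 45% to 25% is (45 − 25)/45 = 44%. It meets the 6A band and not ALR-P.

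**5. What else Table 6A PR needs**

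PR is built on CR. The patient must therefore also be free of leukemia symptoms, have neutrophils above 1 × 10⁹/L and platelets above 100 × 10⁹/L, need no red cell transfusion, and have a normo- or hypercellular marrow. Only the blast component is met automatically. Table 1 in section 5.1.2 sets only lower limits on counts (ANC 500/mcL, platelets 25,000/mcL), so a patient already at CR-level counts is eligible.

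The wording also leaves open whether these conditions govern the 50% decrease limb. If they do, a fall from 60% to 28% (53%) with platelets below 100 × 10⁹/L meets the marrow part of ALR-P but is not 6A PR.

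**6. Effect on the endpoints**

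Sections 4.2.4.1 and 8.2.2 define the AP/BP endpoints as CR or CRi by Table 6A and ALR-P or better by Table 6B. Neither uses Table 6A PR.

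**The case against.** Several stronger readings are tempting, and the case against them is sound.

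- **Opposite commands.** A reader might infer that one section orders a patient off treatment while another orders continuation. Sections 5.8, 7.1.2.5 and 7.1.5.2 all state necessary conditions, which can hold together. Section 7.1.5.2 also applies section 5.8 on top and leaves the decision to the PI. A 6A PR that is not ALR-P is not forced off by section 5.8; it fails section 7.1.5.2 only if both tables must be met and ALR-P is taken as the Table 6B counterpart. What stands is that the text settles neither point, and that sections 5.8 and 7.1.2.5 differ on whether accelerated phase is covered.
- **CI as a rival AP/BP rule.** Section 2.1 is a permissive summary, and footnote h deals with combining visits. Where the rule is given by cohort, CI is paired with MF-CP and PR with AP/BP. These places are better read as MF-CP shorthand, but their wording does not say so.
- **Unchanged disease counted as a response.** No planned efficacy analysis tabulates Table 6A PR, so the documents do not support a claim that a response rate would be inflated.
- **A common event.** Section 5.2.1.2 expects cytopenias at baseline in most subjects, which makes meeting every CR condition less likely. The case is possible; the documents give no frequency.
- **Lost follow-up.** The 30-day safety visit applies to everyone who stops, and Table 8 collects blood at discontinuation for any reason. Extension exposure and later marrow samples are what remain.

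**Conclusion.** The concern holds as an inconsistency in the continuation rule, together with a baseline-free band in Table 6A. Setting the CI wording aside, sections 5.8, 7.1.2.5 and 7.1.5.2 still differ on table and population, and section 7.1.5.2 names a category Table 6B does not contain.

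An unchanged marrow value anywhere from 10% to 25% meets the blast part of Table 6A PR and never meets ALR-P. Full PR also depends on the symptom, count, transfusion and cellularity conditions. The 10-25% result does not depend on where the AP/BP boundary is drawn. It does assume that Table 6A applies to accelerated phase, as sections 5.8 and 7.1.5.2 say and section 7.1.2.5 does not.

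The reach is limited to extension treatment and what follows from it, in at most 10 patients. The primary endpoint concerns another cohort, and the two AP/BP secondary endpoints are not directly changed. The point is still worth correcting before sites apply the gate, because it governs up to 2 years of treatment.

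**What to change.** The sponsor should:

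1. Reconcile sections 5.8, 7.1.2.5, 7.1.4.1 and 7.1.5.2 to one rule that names the table and the category for accelerated phase and for blast phase, and complete the unfinished sentence in section 7.1.4.1.
2. State whether the 6-25% band of Table 6A PR requires a change from baseline.
3. In sections 2.1 and 7.1.5.3.1 and footnote h, limit the CI wording to MF-CP or align it with the reconciled rule.

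This review does not say which rule is right.

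The cost is protocol wording. The planned endpoint analyses need no change. A blanket SAP rule discounting any category whose blast criterion was met at baseline is not advised: a patient who entered on blood blasts with marrow blasts already below 5% could then be barred from counting as CR or CRi, which would alter a secondary endpoint.
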